14.3 Serious Adverse Event

An event that is serious must be recorded on the AE eCRF and on the TI SAE Report Form, and requires expeditious handling to comply with regulatory requirements.

An AE or suspected adverse reaction is considered “serious” if, in the opinion of either the investigator or Sponsor, it results in any of the following outcomes:

- Death; the event must be the cause of death for the SAE to meet this serious criterion.
- Life-threatening event; an event in which the subject was at risk of death at the time of the event and not an event that hypothetically might have caused death if it had been more severe.
- Requires inpatient hospitalization or prolongation of existing hospitalization (for ≥ 24 hours).
- Persistent or significant incapacity or substantial disruption of the ability to conduct normal life functions.
- Congenital anomaly/birth defect.
- Important medical events; a medical event(s) that may not result in death, be life-threatening, or require hospitalization but, based upon appropriate medical judgment, may jeopardize the subject and may require medical or surgical intervention to prevent one of the outcomes listed in the definition above. Examples of such medical events include allergic bronchospasm requiring intensive treatment in an emergency room or at home, blood dyscrasias or convulsions that do not result in inpatient hospitalization, or the development of drug dependency or drug abuse.

Events NOT considered to be SAEs are:

- Hospitalizations for the treatment, which was elective or pre-planned, of a pre-existing condition that did not worsen; and
- Treatment on an emergency, outpatient basis, for an event not fulfilling any of the definitions of “serious” given above and not resulting in hospital admission.

AEs classified as “serious” by either the investigator or the Sponsor require expeditious handling and reporting to TI to comply with regulatory requirements. **All SAEs, whether related or unrelated to IP, must be immediately reported by telephone to the Medical Monitor and, in the event that he/she is unavailable, to the Project Manager listed on the first page of the protocol.** Written notification of all SAEs should be sent to the Project Manager by email or

confirmed facsimile transmission. These include those SAEs listed in the protocol or IB and must include an assessment of whether there is a reasonable possibility that the IP caused the event.

Any suspected adverse reactions that are serious and unexpected represent especially important safety information that must be reported more rapidly to Health Authorities; therefore, it is important that the Investigator submit any information requested by the Sponsor or designee (e.g., TI) as soon as it becomes available.

If only limited information is initially available, follow-up reports are required. Should the investigator become aware of an SAE (regardless of its relationship to IP) that occurs within 30 days after stopping the IP, the SAE must be reported in accordance with procedures specified in this protocol. In the event of death, if an autopsy is performed, a copy of the report should be sent to TI, if available.

As required, the Sponsor or designee (e.g., TI) will notify participating investigators of all suspected adverse reactions that are serious and unexpected. This notification will be in the form of an IND safety report of potential serious risks as soon as possible but no later than 15 calendar days after the Sponsor determines that the information is “reportable” according to the criteria listed in 21 CFR Section 312.32. These are:

- i) Serious and unexpected suspected adverse reactions;
- ii) Findings from other studies including epidemiological studies, pooled analyses, or other clinical studies that suggest a significant risk in humans exposed to the IP;
- iii) Findings from animal or in vitro tests that suggest a significant risk to humans exposed to the IP, or reports of significant organ toxicity at or near the expected human exposure; and
- iv) Clinically important increases in the rate of occurrence of serious suspected adverse reactions.

Upon receiving such notices, the investigator must review and retain the notice with the IB and promptly submit a copy of this information to the responsible IRB according to local regulations. The investigator and IRB will determine if the informed consent requires revision. The investigator should also comply with the IRB procedures for reporting any other safety information. Where required, submission of safety updates by the investigator to Health Authorities should be handled according to local regulations.

The Sponsor or designee may be required to report certain SAEs to regulatory authorities (e.g., United States FDA, National Health Authorities) within 7 calendar days of being notified about the event; therefore, it is important that investigators submit any information requested by the Sponsor or designee as soon as it becomes available.

14.4 Laboratory Test Abnormalities

Any laboratory test results that are outside of normal ranges will be reviewed using the CTCAE version 5.0 classification and by the investigator for clinical significance. Post-baseline, any CTCAE Grade 2 findings or new or worsening clinically significant laboratory test results that meet the criteria for an AE (see [Section 14.1](#)) or SAE (see [Section 14.3](#)) must be recorded on the AE eCRF, in addition to being recorded on the appropriate laboratory test results eCRF and the original laboratory report, as applicable. In these cases, TI will typically require additional information about the clinically significant abnormality, including information regarding relationship to IP, any action taken, and outcome. Clinically significant laboratory abnormalities that qualify as SAEs must be reported to the Sponsor and IRB as per [Section 14.3](#).

Any clinically significant laboratory test result that meets the criteria for an AE (see [Section 14.1](#)) or SAE (see [Section 14.3](#)) must be recorded on the AE eCRF, in addition to being recorded on the appropriate laboratory test results eCRF and the original laboratory report, as applicable. In these cases, TI will typically require additional information about the clinically significant abnormality, including information regarding relationship to IP, any action taken, and outcome. Clinically significant laboratory abnormalities that qualify as SAEs must be reported to the Sponsor and IRB as per [Section 14.3](#).

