12. LABORATORY TESTS

12.1 Blood Chemistry, Hematology, Urinalysis, and Cardiac Biomarkers

Blood and urine specimens will be collected per the SOE for chemistry (including lipid panel and thyroid function), hematology, urinalysis, and cardiac biomarkers. It is preferred that subjects be fasting (approximately 8 hours) for all laboratory assessments; however, if a subject arrives at the clinic without fasting for at least 8 hours, laboratory specimens may be collected as non-fasting, at the discretion of the investigator, and with the appropriate fasting status documented on the lab requisition form. However, the subject must have at least one fasting set of labs prior to treatment being administered on Visit 2/Baseline.

The following laboratory tests will be performed:

LABORATORY TESTS		
Chemistries	Hematology	Urinalysis
Albumin	Hemoglobin	Color
Alkaline phosphatase	Hematocrit	Appearance/Clarity
ALT (SGPT)	MCV	Bilirubin
AST (SGOT)	MCH	Blood
Bilirubin, total	MCHC	Glucose
Calcium	RBC (Erythrocytes)	Ketones
Carbon Dioxide §	WBC (Leucocytes)	Leukocyte Esterase
Chloride	RDW	Nitrite
Creatinine	Differential count	pH
GGT	Basophils	Protein
Glucose (fasting, preferred)	Eosinophils	Specific gravity
LDH	Lymphocytes	Urobilinogen
Phosphate	Monocytes	Microscopic analysis (if indicated)
Potassium	Neutrophils	
Protein, total	Platelets	
Sodium		
Urea (BUN)	Cardiac Biomarkers	
Uric acid	CK-MB	
Lipid Panel	Troponin T	
Cholesterol, total	NT-proBNP	
Triglycerides		
Thyroid Function		
TSH		
Total T3		
Free T4		

§ Bicarbonate may be substituted if the participating lab does not perform assay for carbon dioxide.

Sample collection, handling, labeling, and shipping should be done following the instructions provided by the relevant certified laboratory and the applicable local regulations.

The investigator must review all the subject's laboratory reports in a timely manner. **NOTE:** The investigator will initial and date each laboratory report to indicate his/her review. The investigator

will note, directly on the laboratory report, whether or not any abnormal test results are clinically significant or not clinically significant. Clinically significant laboratory abnormalities that are present at Screening and/or Baseline must be documented in the subject's medical history. In addition, the investigator must complete an appropriate AE form for any new or worsening abnormal test results that are identified as clinically significant after Baseline.

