14.1 Adverse Event Definitions

An **adverse event** is any untoward medical occurrence associated with the use of a drug in humans, whether or not considered related.

An AE (also referred to as an adverse experience) can be any unfavorable and unintended sign (e.g., an abnormal laboratory finding), symptom, or disease temporally associated with the use of a drug, without any judgment about causality. An AE can arise from any use of the drug (e.g., off-label use, use in combination with any drug) and from any route of administration, formulation, or dose, including an overdose.

A **suspected adverse reaction** is any AE for which there is a reasonable possibility that the drug caused the event. "Reasonable possibility" means there is evidence to suggest a causal relationship between the drug and the AE.

An **adverse reaction** is any AE caused by a drug. Adverse reactions are a subset of all suspected adverse reactions for which there is reason to conclude that the drug caused the event. A suspected adverse reaction implies a lesser degree of certainty about causality than adverse reaction, which means any AE caused by a drug. For the purposes of prescription drug labeling, the term adverse reaction means an undesirable effect, reasonably associated with the use of a drug that may occur as part of its pharmacological action or may be unpredictable in its occurrence.

An AE or suspected adverse reaction is considered "unexpected" if it is not listed in the IB or is not listed at the specificity or severity that has been observed. For example, under this definition, hepatic necrosis would be unexpected (by virtue of greater severity) if the IB referred only to elevated hepatic enzymes or hepatitis. Similarly, cerebral thromboembolism and cerebral vasculitis would be unexpected (by virtue of greater specificity) if the IB listed only cerebral

vascular accidents. "Unexpected," as used in this definition, also refers to AEs or suspected adverse reactions that are mentioned in the IB as occurring with a class of drugs or as anticipated from the pharmacological properties of the drug, but are not specifically mentioned as occurring with the particular drug under investigation.

Timely and complete reporting of all AEs assists the Sponsor and/or their designee (e.g., Therapeutics, Inc. [TI]) in identifying any untoward medical occurrence, thereby allowing:

- 1) protection of the safety of study subjects;

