17.3.2 Safety Endpoints

1. Incidence (severity and causality) of any local and systemic AEs.
2. Number of subjects with presence (and severity) of the following LSRs: erythema, edema, erosion, scaling, pruritus, and burning/stinging at each time point.
3. Changes from Baseline in vital signs at each time point.
4. Changes from Baseline in clinical laboratory tests (chemistry [including lipid panel and thyroid function], hematology, and urinalysis, and cardiac biomarkers) at Week 4, Week 8, Week 12, and Week 16.
5. Changes from Baseline in ECG parameters and overall ECG interpretation at Week 4, Week 8, Week 12, and Week 16.

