7.6 Laboratory Tests

Blood and urine specimens will be collected per the SOE for chemistry (including lipid panel and thyroid function), hematology, urinalysis, and cardiac biomarkers. It is preferred that subjects be fasting (approximately 8 hours) for all laboratory assessments; however, if a subject arrives at the clinic without fasting for at least 8 hours, laboratory specimens may be collected as non-fasting, at the discretion of the investigator, and with the appropriate fasting status documented on the lab requisition form. However, the subject must have at least one fasting set of labs prior to treatment being administered on Visit 2/Baseline. Any new or worsening abnormal test results that are identified as clinically significant after Baseline will be recorded as AEs.

The following clinical safety laboratory tests will be performed:

LABORATORY TESTS		
Chemistries	Hematology	Urinalysis
Albumin	Hemoglobin	Color
Alkaline phosphatase	Hematocrit	Appearance/Clarity
ALT (SGPT)	MCV	Bilirubin
AST (SGOT)	MCH	Blood
Bilirubin, total	MCHC	Glucose
Calcium	RBC (Erythrocytes)	Ketones
Carbon Dioxide §	WBC (Leucocytes)	Leukocyte Esterase
Chloride	RDW	Nitrite
Creatinine	Differential count	pH
GGT	Basophils	Protein
Glucose (fasting, preferred)	Eosinophils	Specific gravity
LDH	Lymphocytes	Urobilinogen
Phosphate	Monocytes	Microscopic analysis (if indicated)
Potassium	Neutrophils	
Protein, total	Platelets	
Sodium		
Urea (BUN)	Cardiac Biomarkers	
Uric acid	CK-MB	
Lipid Panel	Troponin T	
Cholesterol, total	NT-proBNP	
Triglycerides		
Thyroid Function		
TSH		
Total T3		
Free T4		

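### The laboratory recording rule in Protocol 14.4 triggers on CTCAE Grade 2 alone, with no higher grades and no Baseline reference, beside three recording rules of different scope

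*Protocol*

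**What the plan says.** Four texts say when a laboratory result becomes an AE.

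- **Protocol 14.4, first paragraph.** Out-of-range results "will be reviewed using the CTCAE version 5.0 classification and by the investigator for clinical significance". After Baseline, the AE form is required for "any CTCAE Grade 2 findings or new or worsening clinically significant laboratory test results", followed by a clause on meeting AE or SAE criteria.
- **Protocol 14.4, second paragraph.** "Any clinically significant laboratory test result that meets the criteria for an AE" or SAE must be recorded. It names no grade and does not require the result to be new or worsening.
- **Protocol 12.1.** The investigator completes an AE form for "any new or worsening abnormal test results that are identified as clinically significant after Baseline". It names no grade.
- **SAP 7.6.** "Any new or worsening abnormal test results that are identified as clinically significant after Baseline will be recorded as AEs". This is the 12.1 rule restated.

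No text ranks these rules, and SAP Section 9 declares no changes to the protocol analysis.

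The first safety endpoint in Protocol 17.3.2 is "Incidence (severity and causality) of any local and systemic AEs". Change from Baseline in laboratory tests at Weeks 4, 8, 12 and 16 is a separate safety endpoint. For laboratory data, SAP 8.9.5 plans listings of all values and shift tables based on whether a value is out of range. It describes no table by CTCAE grade.

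**The concern.** A grade trigger exists so that recording does not rest on site judgement alone. The trigger in 14.4 names one grade. A Grade 2 value gets a route to the AE form by grade, and a worse value does not. The trigger applies to post-baseline findings but does not ask whether the value has changed since Baseline, so a stable pre-existing abnormality could enter the AE table.

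The other three texts have no grade limb, and they differ among themselves on whether the result must be new or worsening. Sites that work from different sections could therefore record different AEs from the same laboratory values.

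The count at stake is laboratory AE incidence. This matters for a thyroid-receptor agonist: Protocol Section 1 cites systemic toxicity concerns for the class, and the schedule includes thyroid, lipid and cardiac-biomarker tests.

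**Working it through.** The documents give no figure on this point, so there is nothing to reproduce. The check is a comparison of the four rules, followed by an illustration of scale.

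**Step 1. What each rule requires, by type of finding** (CS = judged clinically significant)

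| Finding | 14.4 para 1 | 14.4 para 2 | 12.1 and SAP 7.6 |
|---|---|---|---|
| Grade 2, new or worsened, not CS | Required* | Not required | Not required |
| Grade 2, unchanged from Baseline, not CS | Required* | Not required | Not required |
| Grade 3-4, not CS | Not required | Not required | Not required |
| New or worsening and CS | Required if AE criteria met | Required if AE criteria met | Required |
| CS, neither new nor worsening | Not required unless Grade 2* | Required if AE criteria met | Not required |

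*If the AE-criteria clause at the end of the sentence does not also limit the Grade 2 limb. The grammar allows either reading.

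Two results follow.

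1. The first paragraph of 14.4 is not monotone in severity: rows 1 and 2 are triggered by grade, row 3 is not.
2. The rules diverge for Grade 2 findings that are not clinically significant and for clinically significant findings that are neither new nor worsening.

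**Step 2. Can an abnormal Baseline value be present?** Yes. Inclusion criterion 5 asks for normal renal, thyroid and hepatic function only, judged on the Visit 1 results. Other analytes, such as lipids, may be abnormal. Section 12.1 itself provides for clinically significant Screening or Baseline abnormalities to go into medical history.

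**Step 3. Is a lost symbol the cause?** This is not indicated. The ≥ sign survives in the same document, in the hospitalization criterion of Section 14.3.

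**Step 4. Scale.** The plan has about 72 subjects, 24 per group. One subject reclassified in a group changes incidence by 1/24 = 4.2 percentage points.

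The documents give no abnormality rates, so the shares below are assumptions. Let q be the share of subjects with a Grade 2 finding not judged clinically significant. The first paragraph of 14.4, with an automatic Grade 2 limb, then brings in up to n × q more subjects than the other rules:

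| Assumed q | Per group (24q) | Trial (72q) |
|---|---|---|
| 2% | 0.5 | 1.4 |
| 5% | 1.2 | 3.6 |
| 10% | 2.4 | 7.2 |
| 20% | 4.8 | 14.4 |

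For Grade 3-4 findings not judged clinically significant, assumed shares of 0.5%, 1%, 2% and 5% give 72 × share = 0.4, 0.7, 1.4 and 3.6 subjects in the trial. A Grade 2-or-higher trigger would capture them; the literal one would not.

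**The case against.** The strongest reply is that these are inclusion rules. None of the four says that only clinically significant results are recorded. Where the protocol wants an exclusive rule, as for local skin reactions in 10.4.4, it says so. Every site is bound by the whole protocol (18.3) and can comply with all four texts by recording whatever any one of them requires. This stands. A reader might infer that the sections flatly contradict each other, so that the AE table must mix two definitions; the documents support only a risk of uneven recording. Complying with everything still leaves Grade 3-4 without a grade trigger and leaves an unchanged Baseline Grade 2 value recordable.

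A reader might also infer that Grade 3-4 results would go unrecorded. That goes too far. Section 14.1 lets an abnormal laboratory finding be an AE at any grade, 14.2 requires all AEs to be recorded, and 12.1 has the investigator judge every abnormal result. A Grade 3-4 value is missed only if it is judged neither clinically significant nor an AE, which is probably uncommon. If the AE-criteria clause also limits the Grade 2 limb, the contrast between grades is weaker, but Grade 3-4 is still not named.

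Laboratory safety also does not rest on AE coding alone: values are listed, shift tables are planned, and change from Baseline is its own endpoint. This stands as mitigation. It is partial, because an out-of-range flag puts a marginal and an extreme value in the same category.

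Finally, it is tempting to measure the problem by 72 subjects × 4 scheduled post-baseline panels = 288. That is the number of planned panels with full retention, not of affected results.

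**Conclusion.** The point holds as a defect in a stated rule and should be corrected. The grade limb of 14.4 names Grade 2 alone and has no Baseline reference, and the accompanying texts differ in scope with no order of precedence. An intended Grade 2 or higher is a plausible explanation, but that is an inference.

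The effect is confined to descriptive laboratory AE incidence. Randomization is blocked by site (Protocol Section 7), which limits any imbalance between arms from site practice, so the main exposure is in absolute incidence and in comparability across sites. SAP 8.9.6 summarizes whatever AEs are reported, so the mismatch between SAP 7.6 and 14.4 does not itself change a count. No efficacy result is affected, and no formal test is planned.

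The number of affected events cannot be derived from the documents. The illustrative counts depend on the assumed shares, on an automatic Grade 2 limb, and on the subjects concerned having no other recorded laboratory AE.

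**What to change.** 1. Reconcile both paragraphs of Protocol 14.4, Protocol 12.1 and SAP 7.6 into one recording rule. It should state the grade range and say whether AE criteria and clinical significance also apply to graded findings. If a grade trigger is intended, write it as CTCAE v5.0 Grade 2 or higher, new or worsened from Baseline.
2. Merge the second paragraph of 14.4 into that rule. It resembles the first but is not a duplicate: it covers clinically significant results that are neither new nor worsening. Decide explicitly whether those are recorded; simply deleting the paragraph would narrow capture without saying so.
3. Add one SAP table of post-baseline CTCAE v5.0 Grade 2-or-higher values by treatment group, derived from the laboratory data for the analytes that CTCAE grades. That count then does not depend on site judgement.

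The cost is wording changes in the protocol and SAP, one extra programmed table and possibly a few more AE entries. The change concerns recording and tabulation only.

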14.5 Pregnancy

Subjects who are sexually active with a female partner and are not surgically sterile (vasectomy performed at least 6 months prior to treatment) must agree to refrain from sperm donation for at least 90 days following completion of study treatment and inform their female sexual partner to use a highly effective form of birth control as described in the informed consent form. Female partner must be confirmed according to subject to be non-pregnant at Visit 1/Screening and Visit 2/Baseline or at the visit when a subject identifies a new sexual partner. Prior to study enrollment, subjects must be advised of the importance of avoiding pregnancy during study participation and the potential risk factors for an unintentional pregnancy. The subject must sign an informed consent form documenting this discussion.

For female partners of males in the study, highly effective forms of birth control include 1) IUD (copper or hormonal); 2) implantable hormonal contraception; 3) surgical sterilization (i.e., hysterectomy, tubal ligation, or bilateral oophorectomy) performed at least 6 months prior to the subject's study entry; 4) total abstinence; or 5) using one of each of the following a) hormonal contraceptives [other than IUD or implantable, e.g., oral, transdermal, injectable, or vaginal ring] and b) double barrier methods [i.e., male or female condom, diaphragm with spermicidal foam/gel/film/cream/vaginal suppository, cervical cap with spermicides, or contraceptive sponge]. For males, adequate forms of contraception include condom and spermicide in combination with other forms of female contraception.

During the study, all subjects should be instructed to contact the investigator immediately if they suspect that their sexual partner might be pregnant (e.g., female sexual partner has missed or late menstrual period).

If the subject suspects that their sexual partner may be pregnant at any time during the study, or if following initiation of study treatment, it is subsequently discovered that a trial subject's sexual partner was pregnant or may have been pregnant at the time of IP exposure, the investigator must immediately notify the IRB of any pregnancy associated with the study treatment and keep careful source documentation of the event, including abortion (accidental, therapeutic, or spontaneous) and birth of offspring. Offspring should be followed for a minimum of 8 weeks and any congenital anomaly/birth defect in a child born to a subject's sexual partner that was exposed to the IP(s) should be documented.

